Randomization- Patients will be randomized with a probability 2:1 of receiving one of the exercise interventions as compared to usual medical care. The unbalanced design was chosen because we expect a larger functional recovery in both exercise groups as compared to the usual care group requiring higher sample size in these two arms to be able to detect smaller differences between them compared to larger differences from the usual care arm. The study coordinator will carry out the randomization through a web-based computer system at the end of baseline visit, thereby preserving allocation concealment. We

Table 1- Time points and outcome measures of the study	Baseline	Month 3 and 6	Call Month 1.5 & 4.5
Aim 1			
Physical Function (WOMAC-PF & performance tests)	x	x	
Physical Activity (SWA & CHAMPS)			
Aim 2			
Demographics and Biomedical	x		
Medication	x		
Comorbidities	x		
Psychosocial (fear, anxiety, self-efficacy, depression, coping)	x	x	
Physical Impairments (pain, range of motion, muscle strength)	x	x	
Exploratory Aim			
Adverse Events		x	x
Attrition		x	
Adherence with intervention		monitored each visit	
Co-Interventions		x	x

PRINCIPAL INVESTIGATOR (LAST, FIRST, MIDDLE): [name]

will use an adaptive randomization to minimize imbalances in important prognostic variables at baseline including gender, age, BMI, physical function, and knee range of motion. The minimal sufficient balance algorithm⁵² will be used as this method accommodates both categorical and continuous variables. Our data center staff have experience creating this type of randomization algorithm within the framework of the clinical trial database, necessary because the allocation is assigned based on the instantaneous imbalances instead of being generated as a fixed list prior to the beginning of the trial. [name] will monitor randomization and imbalances monthly.

OUTCOMES- The outcomes of this study are entirely patient-centered and selected directly from patient input during structured interviews. They include a broad range of measures as described in Table 1.

Physical Function

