Potential Predictors of Treatment Response- Variables at the baseline that we believe may be potential predictors of treatment response, in addition to physical function (described above) include:

- Demographics and Biomedical Characteristics such as age, gender, race, education, BMI, self-rated health (excellent, good, fair, poor, or bad), discharge placement, number of prior rehabilitation sessions, TKR technique, and surgeon experience will be collected.
- Medication prescribed and over-the-counter used for pain will be recorded in the medication form. We will record the current and highest dosage of any pain medication used during the last month.
- Comorbidity data will be gathered using the Cumulative Illness Rating Scale.⁶⁹ Subjects will be asked to indicate conditions with which they have been formally diagnosed by a physician in the past.
- Psychosocial Measures will include factors that our and other groups have demonstrated to be associated with physical function in knee OA and include:^{48,70-72} 1) Fear; 2) Anxiety; 3) Self-Efficacy; 4) Depression; 5) Coping. We hypothesize that patients with higher fear, anxiety, depression and catastrophizing coping along with low self-efficacy who participated in the community-based group exercise classes will be able to improve physical function, whereas the ones who participated in the individual outpatient exercise will not. Fear-avoidance beliefs will be measured by the Tampa Scale for Kinesiophobia.⁷³ Anxiety will be measured using the Beck Anxiety Index.⁷⁴ Self-efficacy will be measured by the Arthritis Self Efficacy Scale.⁷⁵ Depression will be assessed by the Center for Epidemiologic Studies Short Depression Scale.⁷⁶ Coping will be measured by the Coping Strategy Questionnaire.^{77,78}

PRINCIPAL INVESTIGATOR (LAST, FIRST, MIDDLE): [name]

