For Aim 2, we plan to assess predictors of response based on a minimum change score of 20% in BOTH the WOMAC-PF and the composite score of functional performance at 3 months, thus yielding a binary outcome. For this aim, we will have a combination of those initially randomized to one of the exercise arms and those in the usual care group who were later randomized to the exercise arms for a total of approximately 200. If the expected response rate ranges between 50% and 60%, we would be able to detect an odds ratio of 2.2 to 2.4 with 80% power assuming a binary predictor with 50% split in the sample. In addition, with approximately 100 responders, we will be able to accommodate 9 predictors in the multiple logistic regression based on rule of thumb guidelines for sample size in logistic regression (min of response/nonresponse/ (#predictors+1) \geq 10).

Data Analysis

[name] will oversee data analyses. We will evaluate the statistical properties of baseline and follow-up outcome measures, including potential outliers, normality and missing data. Measures of central tendency (means, medians, other percentiles) and dispersion (standard deviations, ranges) will be computed for continuous variables, whereas frequency distributions will be calculated for categorical data. Distributions of baseline characteristics will be compared between groups to assess effectiveness of randomization, and statistical or clinical differences will be adjusted in the analyses. Data transformations may be applied if needed and guided by clinical meaningfulness.

Hypothesis 1.1 - Subjects in Groups 1 and 2 will demonstrate better physical function as compared to Group 3.

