The primary outcome of this aim is the WOMAC-PF at 3 months.⁹¹ This analysis will use an intention-to-treat approach. We will analyze this aim using contrasts from a linear mixed models analysis for 3 and 6 month function controlling for baseline function and the randomization covariates (age, gender, BMI, physical function, ROM). We will first explore the intervention by time interaction, and then proceed to a main effects model with only group and time. Our primary interest is the 3 month comparison between the clinic-based individual outpatient exercise and the community-based exercise groups. The linear mixed models allow us to maximize the number of individuals used for the analyses as a person can contribute information at both time points, or just one time point. This analysis is advantageous to conducting a simple baseline adjusted ANCOVA at 3 months because persons missing 3 month data would not be included. The linear mixed model “borrows” information pertaining to the relationship between the 3 and 6 month outcomes such that persons missing either (but not both) can still be used in the analyses. To test if the improvements in outcomes are sustained, we will use contrasts from the linear mixed model at 6 months. For missing 3 and 6 month outcomes see missing data section.

For the battery of performance-based tests we will perform the analyses as described above, one for each measure. For these secondary outcomes we will use Hochberg’s step-up procedure to control the experiment-wise Type I error rate ($\alpha=0.05$),⁹² which otherwise would be inflated due to the multiple endpoints. Hochberg’s procedure is more powerful than Bonferroni adjustment and performs well when the number of endpoints is small and correlated with small to mid-size correlations. For this outcome we will also perform analysis using a composite score formed with unit-weighted z scores of constituent tests to provide a more stable measure of the subjects’ underlying functional performance.⁹³

Hypothesis 1.2- Subjects in Groups 1 and 2 will demonstrate increased physical activity as compared to Group 3.

Adjusted analysis for the outcome of physical activity will parallel the analyses described above for performance-based physical function. The outcomes of this hypothesis are real-time physical activity data captured by the SWM and self-reported physical activity from the CHAMPS questionnaire

PRINCIPAL INVESTIGATOR (LAST, FIRST, MIDDLE): [name]

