During our pilot study 100% of the patients completed the 2 month follow-up assessment;¹¹ however we are realistic and recognize that such retention rate is very optimistic for this study. Thus, in this study we estimate the attrition to be 10% at the 3 months follow-up. We also estimate the attrition to be 15% at 6 months, based on our pilot work and other studies with similar populations and timeframes. We will compare baseline characteristics between patients with and without the assessment at 3 and 6 months to assess potential biases in the complete case analysis. We will also try to obtain reasons for study drop out to assess the missing data mechanism (missing completely at random, missing at random, non-ignorable missingness). We will use several missing data methods for imputing data and re-analyze using intention to treat (as randomized) to assess the impact of missing data on our conclusions as recommended.⁹⁷ We

PRINCIPAL INVESTIGATOR (LAST, FIRST, MIDDLE): [name]

will first use multiple imputation (with M=10 imputations) which assumes the data are missing at random. Since the data could be missing not at random, we will use another approach of assigning the lowest observed scores for missing values differentially by treatment group (non-ignorable missingness). The approach assumes the missingness is directly related to the value of the missing data, i.e., the people who are missing data on function have worse function scores (did not come in for assessment because function was worse). Results of all approaches to missing data will be presented in the primary paper for our study. If our significance and interpretation of our treatment effect vary depending on the method of imputation, we will view any conclusions cautiously.

PATIENT POPULATION

Detailed reasoning of inclusion criteria is provided in Human Subjects.

Subjects will be included in the study if they underwent a unilateral TKR 2 to 4 months prior to study, are older than 60 years of age, experience functional limitation in daily activities (score in the WOMAC-PF of at least 9 points), *speak English sufficient to understand study instructions*, are willing to be randomized to one of the 3 treatment groups, and have medical clearance to participate in the study.

Subjects will be excluded if they:

- Have absolute or relative contraindications to exercise testing as established by the American College of Cardiology/American Heart Association;^{99,100}

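### Time since knee replacement, which can range from 2 to 4 months at entry, is not a prespecified covariate in the primary model; the cost is a modest loss of precision

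*Combined protocol and SAP*

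**What the plan says.** The Patient Population section admits people who "underwent a unilateral TKR 2 to 4 months prior to study". The 3-month assessment therefore falls roughly 5 to 7 months after surgery, depending on the patient.

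The Randomization section uses a minimal sufficient balance algorithm to "minimize imbalances in important prognostic variables at baseline including gender, age, BMI, physical function, and knee range of motion". It chose the method because "this method accommodates both categorical and continuous variables".

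Under Hypothesis 1.1, "The primary outcome of this aim is the WOMAC-PF at 3 months", and the mixed model is fitted "controlling for baseline function and the randomization covariates (age, gender, BMI, physical function, ROM". The contrast of main interest is clinic-based versus community-based exercise at 3 months.

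Two further passages bear on the point. The opening paragraph of Data Analysis has baseline characteristics compared between groups and says that "statistical or clinical differences will be adjusted in the analyses". Potential Predictors of Treatment Response gives an open list of baseline characteristics, ending with "discharge placement, number of prior rehabilitation sessions, TKR technique, and surgeon experience will be collected". Time since surgery is not named there, although the surgery date is needed to apply the entry rule.

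**The concern.** Patients are likely to be still recovering when they enter. Two people with the same baseline WOMAC-PF, one 2 months and one 4 months after surgery, may have different amounts of spontaneous improvement ahead of them. Baseline function and range of motion describe the level reached. They probably carry part of the information about stage of recovery, but not necessarily all of it.

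If time since surgery predicts the 3-month score beyond the listed covariates, leaving it out puts that variation into the residual and widens the intervals for every Aim 1 contrast. It also leaves the analyst to decide, after seeing the arms, whether a difference in time since surgery is large enough to adjust for. The plan gives no threshold for that decision.

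**Working it through.** **Inputs from the documents.** Sample Size: 96, 96 and 48 randomised; 86, 86 and 43 expected at 3 months after 10% attrition; SD 7.7; planned differences of 3.3 points (clinic v community) and 5.2 points (usual care v exercise); two-sided alpha 0.05; stated power 81% for the 3.3-point contrast. Patient Population: entry window of 2 to 4 months.

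**Assumptions.**
- Entry is uniform over the window, so the SD of entry time is s = 2/√12 = 0.577 month.
- The slope b, in WOMAC-PF points per month since surgery, is not in the documents and is varied.
- SD 7.7 is taken as the spread before time is added. The plan does not say whether it is adjusted for baseline.
- No allowance is made for the part of the time effect already carried by baseline function.

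**1. The plan's own figure.** Standard error = 7.7 × √(2/86) = 1.174. Power = Φ(3.3/1.174 − 1.96) = Φ(0.850) = 80.2%; the noncentral t gives 79.8%. The stated 81% is reproduced to within about a point.

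**2. Effect of adding the covariate.** Variance explained = (b·s)²/7.7². New SD = √(7.7² − (b·s)²). Power is then recomputed as in step 1.

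| b (points/month) | Variance explained | SD after | Power, clinic v community |
|---|---|---|---|
| not included | – | 7.700 | 80.2% |
| 0.5 | 0.1% | 7.695 | 80.3% |
| 1 | 0.6% | 7.678 | 80.5% |
| 2 | 2.3% | 7.613 | 81.1% |
| 3 | 5.1% | 7.503 | 82.2% |

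A slope of 4 would give 9.0% and 83.8%. If half the patients entered at exactly 2 months and half at exactly 4 (s = 1, the widest possible spread), power would be 80.9%, 82.9% and 86.3% at slopes of 1, 2 and 3.

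**3. Chance imbalance.** The SD of the difference in mean entry time between two arms is s·√(1/n₁ + 1/n₂).
- Clinic v community as randomised: 0.577 × √(2/96) = 0.083 month.
- Usual care v one exercise arm: 0.577 × √(1/96 + 1/48) = 0.102 month.

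A simulation of exponential recovery curves (rates of 0.2 to 0.5 per month, entry WOMAC-PF of at least 9, baseline adjusted) gave time slopes of 0.5 to 2.7 points per month. It is used here only to set a range. At the 95% limit:
- Clinic v community: 1.96 × 0.083 × (0.5 to 2.7) = 0.08 to 0.44 points, or 2% to 13% of 3.3. With 86 completers per arm the range is 0.09 to 0.47.
- Usual care v exercise: 1.96 × 0.102 × (0.5 to 2.7) = 0.10 to 0.54 points, or 2% to 10% of 5.2.

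These shifts are not an extra error. At b = 2 with 86 per arm, the imbalance has SD 2 × 0.577 × √(2/86) = 0.176 points. Its share of the sampling variance is (0.176/1.174)² = 2.3%, the same 2.3% as in the table. The 95% half-width of the contrast is 1.96 × 1.174 = 2.3 points.

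**4. Type I error.** In 20,000 simulated trials per setting (86 v 86, uniform entry, entry time independent of arm), the rejection rate under no effect, without and with the covariate, was 5.1% and 5.1% at b = 2, and 4.7% and 4.8% at b = 3.

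**The case against.** The strongest reply is that the plan already covers this. The Data Analysis rule adjusts for statistical or clinical baseline differences, so it would be wrong to say that an imbalance in time since surgery must go uncorrected. That stands, and the point is limited to prespecification. The rule is weak cover all the same: it acts only on an observed difference, has no stated threshold, recovers nothing when the arms are balanced, and works only if the variable is recorded as a baseline characteristic.

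A second reply is that baseline function and range of motion are both balanced and adjusted for, and plausibly carry part of the recovery stage. This also stands, and it means that each slope in the table may overstate what time adds. In the other direction, if 7.7 is a spread not adjusted for baseline, the residual SD in the model is smaller and a given remaining slope explains a larger share.

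A third reply is that the lists of balancing variables and baseline characteristics are worded as open. True, and their silence does not show that the date is unavailable; the entry rule requires it. The covariate list in the primary model, however, reads as closed, and that is where the specification counts.

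Finally, a two-month window already restricts the variable, and any natural recovery common to both exercise arms cancels on average in the contrast of main interest. Both are fair, and they explain why the effect is small.

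**Conclusion.** The point holds as a minor one. Time since surgery is neither a prespecified covariate in the primary model nor a named balancing variable, and including it would probably sharpen the Aim 1 estimates slightly. Under uniform entry and slopes of 0.5 to 3 points per month, the gain in power for clinic versus community is about 0.1 to 2 percentage points. The size rests wholly on assumed slopes, because the documents contain none.

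A reader might infer more, and the documents do not support it:
- **That natural recovery confounds the comparison.** Randomisation makes the contrasts unbiased, and the simulated type I error is about 5% either way.
- **That a chance imbalance threatens the conclusion.** The 95%-limit shift of about 0.1 to 0.4 points is already within the standard error of the 3.3-point contrast.
- **That the small usual-care arm suffers most.** In points its shift is slightly larger, but as a share of the planned difference it is no larger: 2% to 10%, against 2% to 13%.
- **That a large part of the variance is at stake.** At SD 7.7, even a slope of 2.7 explains only (2.7 × 0.577)²/7.7² = 4.1%.

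**What to change.** Name weeks from knee replacement to randomisation as a recorded baseline variable in the list of demographic and biomedical characteristics. Add it, as a continuous fixed covariate, to the covariates of the mixed model under Hypothesis 1.1, and state that the same applies to all Aim 1 mixed models, including those for performance tests and physical activity. Do this before outcome data are examined by arm.

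Adding the variable to the minimal sufficient balance algorithm is optional and should be considered only if randomisation has not started. The algorithm accepts continuous variables, but balancing adds little once the covariate is in the model.

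The cost is about one sentence in each section concerned and one degree of freedom in each model. No new data collection should be needed, since the surgery date is already required to establish eligibility.

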- **Knee Impairments** – We hypothesize that patients with increased knee pain, decreased knee range of motion, and lower extremity muscle strength who participated in the outpatient rehabilitation will be able to improve physical function whereas the ones who participated in the community-based group exercise classes will not. Knee pain in the surgical and non-surgical knee will also be measured using an 11-point pain scale. Knee range of motion will be measured by a standard goniometer. We will measure the strength of the muscle groups that have been related to the outcome of TKR^{45,79} including knee extension strength and hip abduction strength measured using an isokinetic dynamometer (Biodex System 4 Pro, Shirley, NY) as we described before.⁴⁵

Capturing Potential Harm of Interventions- Growing evidence suggests that regular physical activity does not have deleterious effects on the survival of the prosthesis.^{80,81} The exercises we propose are not expected to cause any harm because they exert relatively low forces over the prosthesis.⁸²⁻⁸⁵ Regardless of the anticipated safety of the exercises, we will ascertain that interventions offer no harm by closely monitoring adverse events:

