Calculations of sample size were based on the primary endpoint of WOMAC-PF at 3 months. We propose to recruit a total of 240 subjects (96 in each exercise arm and 48 in the usual care group) to allow approximately 86 subjects in each exercise arm and 43 in the usual care group available for a complete case analysis at 3 months (assuming 10% attrition at 3 months). We propose a larger number of subjects in both exercises groups (outpatient rehabilitative exercise and community-based group exercise) because we expect a moderate effect size between these two interventions; whereas we propose a smaller number of subjects in the usual care group because we expect a large effect size between the usual medical care group and either of the exercise groups. Thus, with an alpha level of 0.05, 2 tails test, a sample size of 172 (n=86 in each exercise group) will provide 81% power to detect a difference as small as 3.3-point difference between the two exercise groups in WOMAC-PF (SD of 7.7 from our pilot work).¹¹ This would correspond to a difference in less than 2 activities (out of the 17 queried in the WOMAC-PF) having improved from “about moderate difficulty” to “no difficulty”. The sample size of 43 in the usual medical care group will provide 80% power to detect a difference of 5.2-point difference in WOMAC-PF between the usual medical care group and any exercise group. Power analysis was conducted in NCSS/PASS. Moreover, this sample size will provide adequate power (above 80%) to test the hypothesis related to the secondary outcomes (performance-based physical function and physical activity). For example, we will be able to detect differences between the two exercise groups as small as 0.7 sec in the stair climbing test, 0.4 in the chair-rise test, 0.02 m/sec in walking speed, 1.4 sec in the single leg stance, and 35 min/day in light intensity physical activity (based on SD of our own preliminary data). The differences we will be able to detect between the usual care and any intervention groups are as small as 1.01 sec in the stair climbing test, 0.54 in the chair-rise test, 0.03 m/sec in walking speed, 1.6 sec in the

PRINCIPAL INVESTIGATOR (LAST, FIRST, MIDDLE): [name]

single leg stance, and 49 min/day in light intensity physical activity. These differences are smaller than the known minimal detectable changes for these outcomes.⁸⁸⁻⁹⁰

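### Optional efficiency gain: prespecify baseline knee pain and knee-extension strength in the primary WOMAC-PF model, where they could now enter only after an observed imbalance

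*Combined protocol and SAP*

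**What the plan says.** The primary endpoint is WOMAC-PF at 3 months, and the comparison of main interest is clinic-based against community-based exercise. Data Analysis, Hypothesis 1.1, specifies contrasts from a linear mixed model for months 3 and 6, "controlling for baseline function and the randomization covariates (age, gender, BMI, physical function, ROM". The Randomization section uses the same variables (gender, age, BMI, physical function, knee range of motion) in its balancing algorithm.

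Table 1 schedules pain, range of motion and muscle strength at baseline. Under Potential Predictors of Treatment Response, Knee Impairments, pain is scored on an 11-point scale in both knees. Knee extension and hip abduction strength are measured by dynamometer, with this reason: "We will measure the strength of the muscle groups that have been related to the outcome of TKR". For pain the text is weaker. It is a candidate predictor of treatment response, with a hypothesis that it separates responders to clinic exercise from responders to community exercise.

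The opening paragraph of Data Analysis adds that baseline characteristics will be compared between groups and that statistical or clinical differences will be adjusted for. No threshold or variable list is given.

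Sample Size sets the contrast at "with an alpha level of 0.05, 2 tails test", "a sample size of 172 (n=86 in each exercise group", giving "81% power to detect a difference as small as 3.3-point difference between the two exercise groups in WOMAC-PF", with "SD of 7.7 from our pilot work".

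**The concern.** A covariate measured before randomization that predicts the outcome beyond the terms already in the model reduces the standard error of the treatment contrast without biasing it. The plan collects two plausible candidates and uses them only for Aim 2. Range of motion sits beside them in the same impairment hypothesis, yet it is already a covariate in the primary model, so adding the other two would fit the plan's own practice.

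The route that does exist for them, adjustment after an observed difference, selects on chance imbalance rather than on prognostic strength. It also leaves the final primary model open until baseline data by arm have been examined. At stake are a modest amount of precision on the main contrast and a small amount of analyst discretion.

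**Working it through.** **Inputs from Sample Size.** Two-sided alpha 0.05; 86 analysable patients per exercise arm; difference 3.3 points; SD 7.7. Enrolment is "96 in each exercise arm and 48 in the usual care group"; with 10% attrition, 96 × 0.90 = 86.4, which agrees with 86.

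**Reproducing the plan's figure.**
- SE = SD × √(2/n) = 7.7 × √(2/86) = 1.174.
- Standardised difference = 3.3/1.174 = 2.810.
- Normal approximation: Φ(2.810 − 1.960) = 80.2%.
- Noncentral t with 170 degrees of freedom: 79.8%.

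Both are close to the stated 81%. This is an unadjusted two-sample calculation, so the stated power assumes nothing about pain or strength.

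**Assumption.** What matters is the partial R² of pain and strength for 3-month WOMAC-PF, given the planned covariates. The documents do not give it. I take 0, 0.02, 0.05 and 0.10.

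**Cost of two extra terms.** The contrast uses 172 patients. The existing model has 2 arm means and 6 named covariates, so residual degrees of freedom go from 172 − 8 = 164 to 162. Expected variance inflation is (164 − 1)/(162 − 1) = 163/161 = 1.0124, or about 1.2%. I also take 2 off the t degrees of freedom (170 to 168).

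**Net effect.** New SE = SD × √(1 − R²) × √(2/86) × √1.0124, and power comes from the noncentral t. Sample Size does not say whether 7.7 is a raw or a residual SD, so there are two cases:
- Case A: 7.7 is the residual SD under the planned model. Starting power is 79.8%.
- Case B: 7.7 is a raw SD and the planned covariates already explain an assumed 30%. Residual SD = 7.7 × √0.70 = 6.44, SE = 0.982, 3.3/0.982 = 3.36, and starting power is 91.6%.

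| Partial R² (assumed) | Net variance factor (1 − R²) × 1.0124 | Case A power (change from 79.8%) | Case B power (change from 91.6%) |
|---|---|---|---|
| 0 | 1.012 | 79.3% (−0.5) | 91.3% (−0.3) |
| 0.02 | 0.992 | 80.1% (+0.3) | 91.8% (+0.2) |
| 0.05 | 0.962 | 81.3% (+1.5) | 92.6% (+1.0) |
| 0.10 | 0.911 | 83.3% (+3.5) | 93.8% (+2.2) |

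**Break-even.** (1 − R²) × 1.0124 = 1 gives R² = 1 − 1/1.0124 = 0.012, or about 0.01.

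**In patients.** 86/0.962 = 89.4 and 86/0.911 = 94.4. So R² of 0.05 or 0.10 is worth about 3 or 8 more patients per arm after the charge. At R² of 0, 86/1.0124 = 84.9, a loss of about 1 per arm.

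**Limits.** The calculation uses only the two exercise arms at month 3. The planned model also includes usual care and the month-6 data, which I have not modelled.

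**The case against.** The strongest reply is that nothing is wrong. The model adjusts for the baseline value of the outcome and for every variable used in the allocation, which is a coherent, prespecified set. Leaving out further covariates neither biases the estimate nor inflates type I error. All of that stands, and it is why this point is an option rather than a correction.

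A reader might infer several stronger things that the documents do not support:
- *The precision is free and certain.* It is neither. Baseline function and range of motion may already carry most of what pain and strength would add, and Hypothesis 2 itself plans to check collinearity among baseline predictors. At zero added value there is a small loss.
- *The contrast is sized at the edge.* The 79.8% is an unadjusted figure, while the planned analysis is adjusted and borrows month-6 data. If 7.7 is a raw SD, the starting point could be nearer 92%.
- *The plan calls pain prognostic.* It does not. It gives pain a role that differs by exercise arm, which is effect modification. A main-effect covariate gains precision only from prognostic value. The strength statement is general and not conditional on baseline function.
- *The psychosocial scores belong in the primary model too.* The plan says only this: "Psychosocial Measures will include factors that our and other groups have demonstrated to be associated with physical function in knee OA". That is not evidence of added prediction of 3-month WOMAC-PF after knee replacement.
- *The imputation model leaves these variables out.* The missing-data section lists no imputation variables, so it excludes none. That is missing detail and not part of this point.

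It can also be said that the imbalance rule already lets pain or strength in. It does, but only after the data are seen and by an undefined criterion, so it does not replace prespecification.

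**Conclusion.** This holds as a cheap, optional efficiency improvement. Pain and knee-extension strength are collected at baseline, strength is described as related to outcome, and neither is prespecified in the primary model. The validity of the primary analysis and the stated 81% power are unaffected.

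Over the assumed partial R² range of 0 to 0.10, the net change in power for 3.3 points runs from a loss of about half a point to a gain of about 3.5 points in Case A, and from −0.3 to +2.2 points in Case B. Both the partial R² range and the 30% in Case B are assumptions. The sponsor's pilot data, if they include these measures, could narrow them. The benefit that does not depend on those figures is that two variables would no longer enter or stay out of the primary model according to observed imbalance.

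**What to change.** In Data Analysis, Hypothesis 1.1, add one sentence. It should name baseline surgical-knee pain (11-point scale) and baseline surgical-side knee-extension strength as fixed covariates in the primary mixed model, whatever the observed balance. A missing baseline value of either would be replaced by the overall baseline mean across all arms, so that no randomized patient is lost. Fix this before anyone sees unblinded data. If pilot data are available, check first that the two add prediction beyond baseline WOMAC-PF and range of motion. The same check can show whether hip abduction strength, which is also collected, would be the better strength measure; the documents do not rank the two.

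No new data and no extra patient burden are involved. The cost is two model terms, about half a point of power if they add nothing, and the rule for missing baseline values.
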